### **Sample size according to F-test**

Because our main outcomes will be measured at 12 months, we are using pilot work that collected weight loss outcomes at one year. Based on our pilot data (NETworks trial as this provides 12-month outcomes for weight), as well as several other one-year mHealth intervention studies, we calculated the sample size necessary to achieve 95% power (alpha = 0.05) for Aim 1 assuming a small effect size (Cohen's  $d = 0.1$ ) and an intra-cluster correlation (ICC) equal to 0.7. The sample size estimate was 200. For this calculation, we used an F-test on the interaction between time (two levels) and treatment arm (two levels) in a two-way ANOVA with repeated measurements (RM-ANOVA). We used a more conservative value of the ICC as compared to the actual estimate from the NETworks trial data (ICC = 0.9), as the latter would have resulted in a much smaller sample size (for a larger ICC, the residual sum of squares decreases, therefore precision increases and sample size decreases. The opposite is true when the test is strictly between subjects). Further, we assumed an attrition rate between 15 and 20%, and increased the sample size to 240. Thus, we aim to recruit a total of 240 participants (~120 per cohort), with the initial randomization assigning 120 to SocialPOD+points and 120 to SocialPOD-points.

Based on pilot study for overall app usage (Social POD  $50.7 \pm 25.0$  days and standard  $34.4 \pm 25.8$  days out of a possible 84 days) and points earned (mean of  $202 \pm 105$  points/participant with estimated 50 point difference between groups), our power for Aim 2 will be 99% for app usage and 95% for points earned based on our sample size from Aim 1.

We plan to use a random-effects (RE) model which is mathematically equivalent to repeated-measures-ANOVA. However, in the presence of loss to follow-up, RE models can handle responses that are missing at random. RE models can be adjusted for additional covariates if needed (though the randomization procedure should make this unnecessary). RE models provide additional information about the variance of the random effects which is valuable for understanding heterogeneity of responses and assessing the intra-cluster correlation (ICC).

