### **III. Below describes our plans for interim and final analyses and methods for handling missing data:**

#### ***Aims 1 and 2***

Data from all study measures will undergo initial data cleaning to identify potential outliers, determine distributions of variables, assess normality, and enumerate loss to follow-up and other missing data. Descriptive statistics at baseline will be compared between treatment groups to evaluate the success of randomization. ***Analyzing changes in weight between groups at year one***

***(Primary Aims 1):*** For Aim 1, the two levels of the treatment effect will be assignment to SocialPOD+points vs. SocialPOD-points, and the entire study sample will be included. Primary Aim 1 will be addressed using a repeated-measures mixed model with maximum likelihood estimation as provided by PROC MIXED in the SAS® system. Under the assumption that missing data are missing at random, mixed models provide unbiased estimates. These will be adjusted using robust computation of standard errors if non-normality is detected. These models will be estimated applying an intent-to-treat principle. Models for each primary aim are of the same form, with the difference of the groups being compared. Models will examine weight at baseline and at 12 months with a two-level time effect, two-level treatment effect, and two-way interaction between time and treatment. The repeated-measures model will contain time, treatment, time-by-treatment interactions, and any covariates associated with weight loss. Models will be adjusted for changes in PA (via

accelerometers). If the time-by-treatment interaction in a model is significant at the 0.05 level, this will be interpreted as a significant weight-loss effect for one treatment relative to the other.

**Analyzing differences in social support provision and receipt between groups (Aim 2):** For Aim 2, the model will regress support provided (total points earned) and social support received (mean of ratings of support provided to the individual over the 12 months) on treatment group, adjusted for the same covariates used in Aim 1.

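### The covariance structure of the primary weight model is left open, and the missing-at-random claim omits that the covariance must be right; an unstructured covariance is a near-free improvement

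*Combined protocol and SAP*

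**What the plan says.** Two parts of the combined protocol and SAP describe the primary model.

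- **Statistical Design and Power, Sample size according to F-test:** "We plan to use a random-effects (RE) model which is mathematically equivalent to repeated-measures-ANOVA". The same section uses a single ICC (0.7 for planning, 0.9 in the pilot). It prefers the random-effects form because it can handle responses missing at random, and for dropout it states "we assumed an attrition rate between 15 and 20" per cent.
- **Analysis Plan, part III, Aims 1 and 2:** "Primary Aim 1 will be addressed using a repeated-measures mixed model with maximum likelihood estimation as provided by PROC MIXED". No covariance structure is given. On time points: "Models will examine weight at baseline and at 12 months with a two-level time effect". On missing data: "Under the assumption that missing data are missing at random, mixed models provide unbiased estimates". On departures from assumptions: "These will be adjusted using robust computation of standard errors if non-normality is detected". On covariates: "Models will be adjusted for changes in PA".

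The documents give no weight SD at either visit and no expected dropout pattern by arm.

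**The concern.** With two time points, a random-effects model equivalent to RM-ANOVA with one ICC is a random-intercept model: one variance and one correlation, that is, compound symmetry. With complete data this does no harm, because the interaction test is the test on change scores whichever structure is used.

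The plan chose the model for its behaviour under loss to follow-up, and there the structure matters. Likelihood estimates are consistent under missing at random only if the mean and the covariance are both correctly specified. The Analysis Plan states the first half of that condition and omits the second. If the covariance is wrong, dropout that depends only on observed baseline weight, which is ordinary missing at random, can shift the primary contrast and raise its error rate. Robust standard errors would not help: they leave the estimate unchanged, and the plan calls on them only for non-normality.

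**Working it through.** **1. The plan's own figure.** Inputs from the sample-size section: effect size 0.1, ICC ρ = 0.7, alpha 0.05, power 95%, two time points. For the interaction F-test with 0.1 read as Cohen's f, λ = f²·N·2/(1 − ρ).

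- At N = 200, λ = 0.01 × 200 × 2 / 0.3 = 13.3 and power is 95.3%. N = 198 is enough, so the stated 200 reproduces.
- The implied between-arm difference in change is 0.4 baseline SD.
- The figure does not reproduce if 0.1 is Cohen's d, as the plan labels it. That is a separate point.
- The choice of covariance structure does not alter this N. In a complete two-time-point check data set both structures gave the same interaction estimate (0.337), with standard errors of 0.1148 and 0.1155.

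**2. How the structure enters once people drop out.** With baseline complete and 12-month weight missing for some, both models estimate each arm's 12-month mean as

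completer mean + b × (baseline mean of all − baseline mean of completers).

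Compound symmetry sets b to its common correlation. The unstructured model uses the completers' regression slope. The true slope is ρ × (SD at 12 months / SD at baseline). Hence

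bias of the contrast ≈ (true b − compound-symmetry b) × between-arm difference in the completers' baseline shift.

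**3. Inputs.** ρ = 0.9 is the plan's pilot ICC. The rest are assumptions: baseline SD 18 kg, dropout logistic in baseline weight, no treatment effect, no covariates. The SD ratio of 1/0.9 = 1.11 is what ρ = 0.9 implies if change is unrelated to baseline weight. The true b is then 0.9 × 1.11 = 1.0. Maximum likelihood under compound symmetry gives b = 0.893, a gap of 0.107.

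**4. Results (large sample).**

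| Dropout scenario | SD ratio | Difference in baseline shift (SD) | Gap in b | Bias (SD) | Bias at SD 18 kg |
|---|---|---|---|---|---|
| 18% in each arm, odds ratio 1.5 per SD, opposite directions | 1.11 | 0.142 | 0.107 | 0.015 | 0.27 kg |
| 18% in each arm, odds ratio 2 per SD in one arm only | 1.11 | 0.117 | 0.107 | 0.012 | 0.22 kg |
| 12% v 25%, odds ratio 1.5 per SD in both arms | 1.11 | 0.051 | 0.107 | 0.005 | 0.10 kg |
| 18% in each arm, odds ratio 1.5, opposite directions | 1.2 | 0.142 | 0.198 | 0.028 | 0.51 kg |
| 18% in each arm, odds ratio 1.5 in both arms | 1.11 | 0 | 0.107 | 0 | 0 |
| 18% in each arm, odds ratio 1.5, opposite directions | 1.0 | 0.142 | 0 | 0 | 0 |

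The kilogram figures scale in proportion to the assumed SD. In simulated trials of 240 the unstructured model stayed within about 0.03 kg of zero.

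**5. Error rate and power** (6,000 simulated trials of 240).

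| Scenario | Compound symmetry | Unstructured |
|---|---|---|
| Type I error: ratio 1.1, ρ = 0.9, opposite dropout, log-odds 0.5 per SD | 6.1% | 4.6% |
| Type I error: the same with ρ = 0.7 | 5.6% | 4.8% |
| Type I error: ratio 1.2, opposite dropout, log-odds 1.0 per SD, ρ = 0.7 | 9.0% | 5.6% |
| Type I error: the same with ρ = 0.9 | 15.7% | 4.6% |
| Power at 0.4 SD: ρ = 0.7, equal SDs, about 17% dropout unrelated to weight | 96.2% | 96.1% |

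**6. Effect of the physical-activity covariate.** PROC MIXED drops records with a missing covariate. If dropouts have no 12-month physical activity, they leave the model and only completers remain. In such a check data set both structures gave the same estimate, 0.414.

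**The case against.** The strongest reply is that the Analysis Plan, which governs the primary analysis, names no structure, so an unstructured covariance already fits its text. A reader might infer from the sample-size section that the plan forces equal variances. The documents do not support that. The equivalence wording and the single ICC point to a random intercept, but they sit in the sample-size justification. What stands is that one section implies compound symmetry and the other is silent.

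A reader might also infer that 15 to 20% attrition by itself makes the estimate biased. It does not. The contrast is biased only if the SDs differ **and** dropout depends on baseline weight **and** the arms differ in that dependence or in their dropout rate. The documents give none of these inputs. The SD ratio of 1.11 is itself conditional: with correlation 0.9, a baseline–change correlation of (0.9 − 1)/√0.2 = −0.22, meaning heavier people lose somewhat more, gives equal SDs and no bias.

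Finally, the moderate cases are small: 0.015 SD is about 4% of the 0.4 SD design effect. Against the pilot's three-month difference of 5.3 − 2.2 = 3.1 kg, 0.27 kg is about 9%. Error rates of 9 to 16% need an extreme pattern. All this limits the size of the point. It gives no reason to keep compound symmetry or the unqualified sentence.

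**Conclusion.** The point holds as a minor one. The primary model's covariance is implied in one section and unstated in the other, and the claim of unbiasedness omits a necessary condition. Under the assumptions above (baseline SD 18 kg, correlation 0.9, SD ratio 1.11, about 18% missing), compound symmetry biases the contrast by about 0.1 to 0.3 kg, with type I error up to about 6%. With equal SDs, with dropout unrelated to baseline weight, or with the same dropout pattern and rate in both arms, the bias in the contrast is zero.

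A reader might infer that the unstructured covariance is a complete cure. It is not:

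- It acts only on participants kept in the likelihood, and adjustment for change in physical activity removes anyone without a 12-month value.
- The 6-month weight is collected but not modelled, so dropout that depends on it is not missing at random given the modelled data.
- A pooled unstructured covariance still assumes the same covariance in both arms.

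**What to change.** 1. In the sample-size section and in Analysis Plan part III, specify the two-time-point primary model with an unstructured covariance, for example `REPEATED time / SUBJECT=id TYPE=UN` in PROC MIXED, in place of the random-intercept description.
2. Reword the missing-data sentence to say that estimates are unbiased under missing at random *given a correctly specified mean and covariance*.
3. Leave change in physical activity out of the primary model, so that dropouts with a baseline weight stay in the likelihood. Without this step the change of structure has only partial effect, or none.

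REML and Kenward-Roger degrees of freedom are optional; nothing here shows a need for them at N = 240.

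The cost of the covariance change is one line of code, some SAP wording and one extra covariance parameter. The required sample size does not change, and power at 240 is 96.1% against 96.2%.

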## **Analysis Plan**

### **I. Below details how the outcomes will address the hypotheses being tested:**

We have two main hypotheses in this study. We are examining our outcomes among 240 adults with overweight or obesity and  $\geq 3$  T2DM risk factors.

Hypothesis 1: That the SocialPOD+points group will lose significantly more weight than the SocialPOD-points group.

Hypothesis 2: That the SocialPOD+points group will have greater objectively measured levels of social support provision and receipt than the SocialPOD- group

In order to ensure that each of these hypotheses can be addressed we must measure the following outcomes:

Objective body weight assessments

Objective assessment of social support provision and receipt via the app

Type 2 diabetes risk factors (assessed at baseline, 6 months, and 12 months): body weight, body circumference measures, and blood pressure

Demographic data (race/ethnic group and sex)

These outcomes will help us examine how weight loss and social support provision and receipt may differ between groups.

### **III. Below describes our plans for interim and final analyses and methods for handling missing data:**

#### ***Aims 1 and 2***

Data from all study measures will undergo initial data cleaning to identify potential outliers, determine distributions of variables, assess normality, and enumerate loss to follow-up and other missing data. Descriptive statistics at baseline will be compared between treatment groups to evaluate the success of randomization. ***Analyzing changes in weight between groups at year one***

***(Primary Aims 1):*** For Aim 1, the two levels of the treatment effect will be assignment to SocialPOD+points vs. SocialPOD-points, and the entire study sample will be included. Primary Aim 1 will be addressed using a repeated-measures mixed model with maximum likelihood estimation as provided by PROC MIXED in the SAS® system. Under the assumption that missing data are missing at random, mixed models provide unbiased estimates. These will be adjusted using robust computation of standard errors if non-normality is detected. These models will be estimated applying an intent-to-treat principle. Models for each primary aim are of the same form, with the difference of the groups being compared. Models will examine weight at baseline and at 12 months with a two-level time effect, two-level treatment effect, and two-way interaction between time and treatment. The repeated-measures model will contain time, treatment, time-by-treatment interactions, and any covariates associated with weight loss. Models will be adjusted for changes in PA (via

accelerometers). If the time-by-treatment interaction in a model is significant at the 0.05 level, this will be interpreted as a significant weight-loss effect for one treatment relative to the other.

**Analyzing differences in social support provision and receipt between groups (Aim 2):** For Aim 2, the model will regress support provided (total points earned) and social support received (mean of ratings of support provided to the individual over the 12 months) on treatment group, adjusted for the same covariates used in Aim 1.

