## **Overview of assessments**

Potential participants will be directed to a study website to learn more about the study and complete a screening questionnaire. If they qualify, they'll be invited to an orientation session where they'll learn more and sign a consent form. Participants will then complete online surveys measuring psychosocial variables and diet, and anthropometric data will be collected. Those who complete all baseline assessments will be randomly assigned to either the mLIFE+points or mLIFE group using a computer program allocation sequence, stratified by sex and baseline BMI (to ensure equal distribution of sex and weight classes among the two groups). All participants will complete assessments at baseline, 6, and 12 months. The study will involve two cohorts, each with 120 participants, staggered by 12 months.

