## Assessments

Participants' assessments will be conducted at baseline, 6, and 12 months of the intervention. The following table and cited references describe the surveys and measurements conducted at each time point:

Instrument	BL	6 mo	12 mo
Demographic, social support and potential mediators/moderators			
Demographic and socioeconomic status			
Demographic variables	X		
Socioeconomic status variables, use of nutrition assistance programs, environmental changes	X	X	X
Current medications	X	X	X
Social support provision, receipt and enjoyment			
Number of times a person completes a social support-related activity (SS provision)		X	X
Adapted Multidimensional Scale of Perceived Social Support Scale (MSPSS) – (SS perceived) 		X	X
Ratings each participant gives to the social support provided to them after they request support (SS perceived)		X	X
Total number of times other participants provided support to the individual (SS receipt)		X	X
EGameFlow (enjoyment) 		X	X
User engagement and user burden			
User Engagement Survey* (adaptation) 	X	X	X
User Burden Scale* (adaptation) 	X	X	X
Self-efficacy and -regulation and motivation			
Weight Efficacy Life-Style Questionnaire (WEL-Q) 	X	X	X
Treatment Self-Regulation Questionnaire (TSRQ) 	X	X	X
Potential drivers of weight loss			
NCI's Automated Self-Administered 24-hour Dietary Recall (ASA24®) – 3 unannounced recalls – two weekdays, one weekend day) 	X	X	X

Physical Activity (FitBit tracker) – minutes per week of MVPA (min:10h/d, 3 valid days) 	X	X	X
Exercise Vital Sign Questionnaire 	X	X	X
The Stanford Leisure-Time Activity Categorical Item (L-Cat), short version 	X	X	X
Physiological and anthropometric measures			
Height (self-report) / weight (FitBit Aria Scale) 	X	X	X
Hip and Waist circumference (self-report).	X	X	X
T2DM (Type 2 Diabetes Mellitus) risk factors (risk score 0 – 10)	X	X	X
Self-monitoring adherence and study compliance/responsiveness			
Monthly survey (self-monitoring)		X	X
Adherence to FitBit devices usage (mLife app – rewards or points)		X	X
Adherence to self-monitoring diet (mLife app - logging $\geq 2$ eating occasions per day)		X	X
Use of intervention components (mLife app - use of all intervention components)		X	X
Factors that may affect compliance: differential dropouts and reasons to discontinue the study		X	X

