## Body-weight

Body weight is determined objectively and self-reported, with units for assessment reported in pounds (lb). The self-reported body weight is one of the first questions in the “health status” survey.

For the objective measure, participants receive instructions on how to use the provided Fitbit Aria Air scale, which syncs data to the Fitbit app. If the scale does not properly sync to their Fitbit app, participants are asked to take a picture of the scale's display and upload it to the instrument for data verification (self-reported, verified).

At the beginning of the trial, the first synchronized body weight reading is recorded as baseline. The body weight at 6 months and 12 months is determined as the last reading at weeks 26 and 52, respectively. The objective measure of body weight data is extracted from Fitbit and is pulled to the mLife site, from where it is exported to a CSV file. The body weight and date are then imported to RedCap at the assessment event using the “Body Weight (Fitbit)” instrument. Importing the body weight data marks the instrument as “complete,” so it

is not requested again from the participant. However, if no body weight data is reported for a participant at the end of the assessment period, they receive a link to either report their body weight directly to the form “Body Weight (Fitbit)” or to manually enter it into their Fitbit profile. In either case, they are prompted to upload a picture of the scale.

Participants follow the instructions below to get their body weight reading. These instructions are included in the RedCap instrument for the participant.

- Use Aria Air while barefoot.
- Make sure your feet are dry before weighing yourself.
- Place Aria Air on a hard, flat surface during use.
- Balance your weight evenly between both feet when you stand on the scale.
- Weigh yourself at the same time each day to see consistent trends. Your weight naturally varies over the course of the day.

---

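### The primary weight model relies on missing at random but leaves out the scheduled 6-month weight, so dropout that depends on 6-month progress is not covered

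*Combined protocol and SAP*

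**What the plan says.** Analysis Plan, part III (Aims 1 and 2) defines the primary model: "Models will examine weight at baseline and at 12 months with a two-level time effect", a two-level treatment effect and their interaction, estimated by maximum likelihood in PROC MIXED. On missing data it says "Under the assumption that missing data are missing at random, mixed models provide unbiased estimates". It also says "Models will be adjusted for changes in PA", without stating how that change is coded.

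The section on sample size by F-test repeats the two-level design and the reliance on missing at random. It also says "we assumed an attrition rate between 15 and 20" per cent.

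The 6-month weight exists by design. The synopsis states "All participants will complete assessments at baseline, 6, and 12 months". The Assessments table marks scale weight at all three visits, and the Body-weight section fixes the definition: "The body weight at 6 months and 12 months is determined as the last reading at weeks 26 and 52, respectively".

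No section brings the week-26 weight into the primary model as a response, a covariate or an imputation variable. The openings for further covariates (Analysis Plan, parts III and V) do not name it. No imputation and no sensitivity analysis for departures from missing at random is described.

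**The concern.** A likelihood analysis is valid under missing at random only with respect to the data the model contains. In the two-point model, a participant without a 12-month weight contributes a baseline weight and nothing else. If people who had lost little by month 6 are more likely to leave, those who remain at month 12 are a selected group, and baseline weight does not correct for that. The reading that would correct for it is collected but not used.

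At stake is the 12-month difference between arms, the trial's main result. Selection of the same strength in both arms cancels. If it differs by arm, the estimate moves, in either direction. The arms differ in a feature meant to sustain engagement (points, leaderboard, newsletter recognition), so differential dropout is possible, though the documents do not establish it.

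**Working it through.** **1. The plan's own figures.** The interaction F-test has noncentrality f²·N·m/(1-ICC). With 0.1 taken as Cohen's f, N = 200, m = 2 times and ICC = 0.7, this is 0.01 × 200 × 2 / 0.3 = 13.3. Power is 95.3%, and the smallest N for 95% is 198, so the stated 200 reproduces. (The plan labels 0.1 as Cohen's d; that is a separate matter.) With 240 randomised, 15% attrition leaves 240 × 0.85 = 204 and 20% leaves 240 × 0.80 = 192, with power 95.6% and 94.5%. Attrition is therefore covered for power. The question here is bias.

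**2. What the two models use.** In each arm, the two-point estimate of the 12-month mean is the observed 12-month mean plus b × (baseline mean of all - baseline mean of those observed). The three-point model adds the corresponding term for week-26 weight. Dropout driven by 6-month change is ignorable only in the second.

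**3. Assumed inputs.** Only the 15-20% attrition comes from the documents; its midpoint, 17.5%, is about 240 × 0.175 = 42 people. The rest is assumed:
- Mean change is -3.5 kg (mLife) and -5.75 kg (mLife+points) at month 6, then -4.0 and -7.0 kg at month 12, so the true difference is -3.0 kg.
- All dropout comes after month 6, with log-odds rising by 0.5 or 1.0 per 5 kg less loss at month 6.
- There are four covariance matrices. A and B: change independent of baseline, change SDs 5 and 7 kg, correlation between changes 0.6 and 0.8. C and D: equal SDs over time, ICC 0.9 and 0.7, scaled to a 12-month change SD of 7 kg.

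**4. Hand check (informative dropout in the mLife arm only, slope 0.5).** The slope is 0.5/5 = 0.1 per kg. To first order, the mean 6-month change among those who stay shifts by -0.175 × 0.1 × 5² = -0.44 kg. The regression of 12-month on 6-month change is 0.6 × 7/5 = 0.84 (A) or 0.8 × 7/5 = 1.12 (B). The mLife arm then appears to have lost an extra 0.37 or 0.49 kg, giving differences of -2.63 and -2.51 kg. Simulation gives -2.66 and -2.52.

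**5. Simulation (1,000,000 per arm; Monte Carlo error about 0.01-0.02 kg; ranges over A-D and both slopes, except the first row, which is slope 1.0).**

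| Dropout after month 6 | Two-point estimate (kg) | Bias |
|---|---|---|
| Equal slopes and rates | -3.00 to -3.03 | 0% within error |
| One common rule for both arms | -2.94 to -2.74 | 2-9%, toward no effect |
| Both informative, one slope twice the other | -2.75 to -2.61, or -3.25 to -3.37 | 8-13%, either direction |
| Informative in mLife only | -2.67 to -2.16 | 11-28%, toward no effect |
| Informative in mLife+points only | -3.33 to -3.87 | 11-29%, away from no effect |

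The three-point unstructured model gives -2.97 to -3.02 throughout. These three-point fits used a common baseline mean. A separate simulation without that constraint (effect 0.40 SD, ICC 0.7, 15% or 20% dropout) had three-point bias within 0.003 SD. Its two-point bias was 0.030-0.038 SD under a common rule, and type I error was 10-16% with one-arm informative dropout and no true effect.

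**6. What limits the gain (one-arm cases).**
- If 40% of dropout comes before month 6, the three-point model leaves 4-10%.
- With a random intercept only, it leaves 3-17%, because equal correlations are forced on three times.
- If change in physical activity enters as one 12-month value per person and dropouts have none, their records are deleted along with the week-26 weights, and 11-29% remains.

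**The case against.** The strongest reply is that the large figures need dropout that is informative in one arm only and occurs entirely after week 26. The documents give neither a mechanism nor a timing. Under one common rule the bias is 2-9%; with equal slopes and rates it is nil. This stands, and it sets how the size should be reported. The percentages also depend on the assumed -3.0 kg. The plan's design effect is 0.4/0.775 = 0.516 SD of change, or 3.6 kg at a change SD of 7 kg, and the one-arm range at 17.5% missing is then 9-24%.

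Attrition is also not the same as missing weight. Assessment-only participants are still contacted, photo-verified weights are accepted, scale problems are followed up and the reading is paid for. The plan also records differential dropout and its reasons. These should reduce the missing share, but none of them repairs the model.

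Two stronger readings are tempting. A reader might infer that adjusting for physical activity would cancel any benefit of adding week 26. That is a worst case: the coding is unspecified, and the Physical activity section allows data from two weeks before or one week after the cutoff, so a participant with no 12-month weight may still have an activity value. A reader might also infer that the arms must be constrained to a common baseline mean, with baseline readings restricted to dates before allocation is revealed, because "At the beginning of the trial, the first synchronized body weight reading is recorded as baseline" sets no date limit. The plan already places baseline completion before the reveal. Fitbit profiles are linked to the app at the session that reveals allocation, so such a filter could discard an unknown number of baseline weights. Both are optional.

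**Conclusion.** The gap is real. The primary model leaves out a scheduled weight that would make dropout related to 6-month progress ignorable, and it relies on missing at random without it. The size is unknown and may be zero. On the assumptions above, it is 0% with equal slopes and rates, about 2-9% under one common rule, and 11-29% in either direction only with one-arm informative dropout.

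A reader might infer that the 12-month estimate will be biased by up to 29%. The documents do not support that, because they do not show that dropout depends on 6-month weight, that it differs by arm, or that it falls after week 26. Nor is week 26 a complete answer: it does not help with dropout before month 6 or with data not missing at random. The case for change is that the improvement is cheap and uses data already planned.

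**What to change.** - Fit the maximum-likelihood repeated-measures model to baseline, 6- and 12-month weight, with three-level categorical time, treatment, their interaction and unstructured covariance (not a random intercept alone). Keep the 12-month treatment contrast as the single primary test.
- Do not condition the primary model on a participant-level 12-month change in physical activity, so that dropouts' week-26 weights stay in. Report that adjustment as a secondary analysis.
- Add a sensitivity analysis for departures from missing at random.
- Make the change before 12-month data are examined unblinded. Much of the conduct is described in the past tense and cohort 2 training was in July 2023, so this may no longer be possible. In that case, report the three-point model as a fully specified sensitivity analysis beside the planned one.

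The cost is SAP text and PROC MIXED code, slightly more analysis work and a larger covariance structure to estimate. No new data are needed.
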